## 6.2 Safety endpoints

Treatment-emergent period is defined as the time from first study treatment intake up to 6 weeks (inclusive) after last study treatment intake.

- Treatment-emergent AEs, SAEs, and AESIs#;
- AEs leading to premature discontinuation of study treatment;
- Changes in 12-lead ECG variables (HR, PR, QRS, QT, QT corrected for heart rate on the basis of Bazett's formula [QTcB] and QT corrected for heart rate on the basis of Fridericia's formula [QTcF]), from pre-dose to selected post-dose assessments (1 h, 2 h, 3 h, 4 h, 5 h, 6 h) on Day 1 and on day of study drug re-initiation;
- Occurrence of treatment-emergent 12-lead ECG outliers (e.g., HR, PR, QTc defined in the Statistical Analysis Plan [SAP]);
- Occurrence of treatment-emergent 12-lead ECG abnormalities;
- Occurrence of treatment-emergent ECG-Holter abnormalities on Day 1;
- Change in SBP and DBP from baseline up to EOS;
- Change in FEV1 and FVC, expressed in absolute value (L) and percent value from baseline up to EOS;
- Occurrence of treatment-emergent decrease of FEV1 or FVC > 15% from baseline values;
- Change in laboratory parameters (hematology, blood chemistry, and urinalysis) from baseline up to EOS;
- Treatment-emergent laboratory abnormalities according to CTCAE 2010 v4.03 [CTCAE 2010] and FDA guidelines [FDA 2009] (for ALT/AST/TBL);
- Change in protein-to-creatinine ratio from baseline to EOT;
- Change in body weight from baseline to EOT.

#AESI considered for the analyses are described in [Appendix 3](#).

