### 5.8.10 Laboratory

Laboratory test results are transferred from the central laboratory or, if assayed locally, entered in local laboratory eCRF. Assessments are performed at each scheduled visit from Visit 1 (Screening) to Visit 7 (EOS), and at unscheduled visits if required.

The following parameters are assayed:

- **Hematology:** Hemoglobin, hematocrit, platelets, MCH, MCV, MCHC, reticulocytes/erythrocytes, erythrocytes, leukocytes count with differential count (basophils, eosinophils, lymphocytes, neutrophils, monocytes, and basophils/ leukocytes, eosinophils/ leukocytes, lymphocytes/ leukocytes, monocytes/ leukocytes, neutrophils/ leukocytes);
- **Blood chemistry:** Aspartate aminotransferase (AST), alanine aminotransferase (ALT), alkaline phosphatase, total bilirubin (TBL), direct bilirubin, lactate dehydrogenase, creatinine, blood urea nitrogen, urate, glucose, cholesterol, triglycerides, sodium, potassium, chloride, calcium, protein, albumin, creatinine clearance;
- **Coagulation tests:** prothrombin time, INR, activated partial thromboplastin time;
- **Urine protein-to-creatinine ratio** (Visits 1, 2 and 6): Creatinine, protein, protein/ creatinine.

For women of childbearing potential, serum pregnancy tests are performed at Visit 1 (Screening) and Visit 7 (EOS) (central laboratory), and urinary pregnancy tests are performed at all other visits and collected in the dedicated eCRF page.

Urine dipsticks are used to perform the urinalysis at all visits (e.g., pH, glucose, proteins, blood, leukocytes) and the results are recorded in the dedicated eCRF page.

The following endpoints are defined:

- Absolute value and absolute change from baseline in laboratory parameters (hematology, blood chemistry, and urinalysis) at each post-baseline analysis visit up to EOS;
- Treatment-emergent laboratory test abnormalities based on reference ranges (central laboratory) and abnormality thresholds (as defined in appendix 7 of the study protocol and in Section 15.2).

For these abnormalities, additional criteria are defined to characterize the occurrence of treatment-emergent abnormalities during the treatment period in each direction separately (low and high).

Treatment-emergent liver function abnormalities occurring at any time post-baseline are identified according to the following criteria, where a subject is considered to have met the criteria if they have at least one abnormality based on the worst post-baseline value measured (up to EOS):

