### **10.9 Analysis of safety variables**

The SAF is used to perform all safety analyses.

For the tabulations by analysis visit and time points (e.g. values over time for blood pressure measurements, ECG), if multiple values are available (unscheduled visits/retests), the examination closest to the planned visit/ time point is chosen [see Section 11 for more details].

However, for the summaries of treatment-emergent abnormalities over the study period, all safety data collected up to EOS are considered.

All safety data are included in listings, with specific flags for the treatment-emergent or values taken into account in the analyses.

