#### 10.9.4 Laboratory tests

Descriptive summary statistics by analysis visit and treatment group are provided for observed values and absolute changes from baseline by category (hematology/ coagulation, chemistry, urinalysis). Data are displayed in SI units as provided by the central laboratory.

Values from local labs are not included in the different summaries but are included in the listings.

For categorical urinalysis parameters (dipstick), qualitative descriptive statistics for recorded values are presented by parameter and visit.

Treatment-emergent laboratory abnormalities are summarized by lab category, parameter and severity over the study treatment period. For each parameter, the severity is based on the position of the value against reference ranges (central laboratory) and additional thresholds for significance (see appendix 7 of the study protocol) and the worst abnormality is considered in each direction separately (Low and High). In addition, for the liver tests, the number and percentages of subjects with values above the normal ranges, or with abnormal values that are of a certain size (e.g., twice the upper limit of the normal ranges; see section 5.1.10.5, figure 3 of the study protocol) are presented along with their 95% Clopper-Pearson confidence intervals. For each parameter, the maximum highest value recorded during the treatment period is taken into account.

The denominator for percentages is the number of subjects with at least one post-baseline assessment.

All data are presented in the listings:

- hematology, chemistry, coagulation, urinalysis
- urinary dipstick
- viral serology (if assay is required)/ tuberculosis test results are listed along with the other baseline characteristics

- serum and urinary pregnancy tests results are listed along with the childbearing potential information

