#### 10.9.5 Vital signs and body weight

For body weight, a summary table presenting the value at baseline, value at Visit 6 (EOT) and the change from baseline is produced by treatment group.

Standing SBP and DBP (mmHg) are not included in the summary tables but included in the listings.

For supine SBP and DBP (mmHg), the following displays are provided:

- Quantitative descriptive statistics for absolute values by treatment group and analysis visit and time point.
- Quantitative descriptive statistics for the absolute change from baseline to 1h, 2h, 3h, 4h, 5h and 6 h post-dose on Day 1 and each post-baseline analysis visit by treatment group and parameter. This table is repeated for the measurements taken on day of study drug re-initiation, if applicable.
- Boxplots of absolute values at baseline and all post-baseline analysis visits and time points: one figure per parameter and per treatment group. Notable abnormality thresholds are displayed on the plots as an overlay.
- Notable BP abnormalities are summarized by treatment group by presenting the number and percentage of subjects with any abnormality at each post-baseline analysis visit and time point, at any time on Day 1 (from 1 hour post-dose to discharge), at any time after Day 1 (from discharge on Day 1 up to EOT), and at any time post-baseline (from 1 hour post-dose to EOS), 95% Clopper-Pearson confidence intervals are presented for the proportions.

The denominator for percentages is the number of subjects with at least one post-baseline assessment in the considered interval.

All data (values and changes) are listed by treatment group, subject and visit. All marked abnormalities are flagged.

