### 11.2.17.1 *Blood pressure*

For Supine SBP / DBP (mmHg):

**Baseline** is defined as the mean (computed in the eCRF) of the 2 measurements performed on Visit Day 1, at pre-dose (Category equal to 'MEAN'). If missing, it is replaced by the last non missing value recorded prior to the first dose.

**Analysis value** is defined as the value at the visit/ time point (numeric result in standard units). For assessments performed on Visit Day 1, after pre-dose, the analysis value at the time point is retrieved from the record available. For all visits performed after Day 1, the analysis value is retrieved from the record populated with VSCAT = 'MEAN'.

Abnormalities, as defined in table 'treatment emergent notable abnormalities' are populated for each post-baseline assessment individually. In addition, the occurrence of at least one 'Low' and at least one 'High' treatment-emergent abnormality is derived on the subject level for the following time intervals: on Day 1 (from 1 hour post-dose up to discharge), after Day 1 (from discharge on Day 1 through Visit 7 (EOS)) and at any time post-baseline.

For Standing SBP / DBP (mmHg), only the **Analysis value** at the visit is populated.

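### The SAP ends the window for liver and other laboratory abnormalities at two different points, and one blood-pressure derivation runs to EOS where three other places stop at EOT or Week 12

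*SAP*

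**What the plan says.** **Liver tests.** SAP 5.8.10 classifies a subject as meeting a liver criterion "based on the worst post-baseline value measured (up to EOS". SAP 10.9.4, which specifies the liver table and its Clopper-Pearson intervals, says: "For each parameter, the maximum highest value recorded during the treatment period is taken into account".

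**Other marked laboratory abnormalities.** Here the two laboratory sections agree with each other. In SAP 5.8.10, "additional criteria are defined to characterize the occurrence of treatment-emergent abnormalities during the treatment period in each direction separately (low and high". In SAP 10.9.4, "Treatment-emergent laboratory abnormalities are summarized by lab category, parameter and severity over the study treatment period".

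**General safety rules.** SAP 10.9 states that, for summaries of treatment-emergent abnormalities over the study period, "all safety data collected up to EOS are considered". SAP 7.1.4 gives EOS as the default cut-off for the safety set. In Protocol 6.2, "Treatment-emergent period is defined as the time from first study treatment intake up to 6 weeks (inclusive) after last study treatment intake". Protocol 11.3.3 repeats that definition, and Protocol 11.4.3 makes it the default for safety tables and figures.

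**Blood pressure.** For the interval after Day 1, SAP 10.9.5 has "at any time after Day 1 (from discharge on Day 1 up to EOT". SAP 5.8.6.1 also stops at EOT, and the analysis record in SAP 11.1.1 stops at Week 12. The derivation in SAP 11.2.17.1 has "after Day 1 (from discharge on Day 1 through Visit 7 (EOS".

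**The concern.** A programmer cannot satisfy both liver sentences, because they give different end points for the same summary. For the remaining laboratory parameters the specific sentences are narrower than the general rules above them. They are also narrower than the protocol, and nothing in SAP section 4, which records changes and clarifications, says that this was intended.

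Safety and tolerability is one of the two main objectives. Under the narrow wording, a liver or hematology abnormality that first appears at a completer's EOS visit would not be counted in the treatment-emergent incidence tables, although the protocol's definition covers it. If the wording stays open, the choice falls to programming and could be made after unblinding.

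The blood-pressure discrepancy runs the other way. An interval meant to describe readings on treatment after Day 1 would take in the follow-up visit.

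**Working it through.** **1. Passages side by side**

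| Data | Treatment period, EOT or Week 12 | EOS or 6 weeks after last intake |
|---|---|---|
| Liver criteria | SAP 10.9.4 | SAP 5.8.10, 10.9, 7.1.4; Protocol 6.2, 11.3.3, 11.4.3 |
| Other laboratory (low/high) | SAP 5.8.10, 10.9.4 | SAP 10.9, 7.1.4; Protocol 6.2, 11.3.3, 11.4.3 |
| BP, after Day 1 | SAP 5.8.6.1, 10.9.5, 11.1.1 | SAP 11.2.17.1 |
| BP, any time post-baseline | none | SAP 5.8.6.1, 10.9.5 |

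The laboratory derivation section, SAP 11.2.15, gives no end date and so does not settle the matter. The parallel ECG derivation, SAP 11.2.11, ends its after-Day-1 interval at EOT, so 11.2.17.1 stands alone.

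**2. The plan's own figure.** SAP Table 11 gives Day 127 as the EOS target. Week 12 is 12 × 7 + 1 = Day 85 (there is no Day 0), and 85 + 6 × 7 = Day 127, which reproduces it.

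**3. Size of the disputed window for a completer**
- Treatment period read as the protocol's 12 weeks (Protocol 3.1.1.2): 12 × 7 = 84 days. To EOS: 84 + 42 = 126 days. The difference is 42 days, and 42/126 = one third.
- Treatment period read as Table 11's treatment phase, which ends on Day 105: with a last dose on Day 84, Days 106 to 126 are excluded, that is 21 days or about three weeks.
- Under either reading the EOS visit is excluded. It is one of five scheduled post-baseline laboratory visits (Weeks 2, 4 and 8, EOT, EOS).

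**4. Early stoppers.** Table 11 assigns a value to EOS only if it falls after Day 105 or more than 42 days after last intake. A subject who stops on Day 30 and has the EOS sample on Day 72 is exactly 42 days out, so that sample falls in the Week 12 window (Days 71 to 105). A completer's EOS sample at Day 127 does not. The Table 11 reading therefore treats completers and early stoppers differently.

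**5. Effect on a reported incidence.** The number of subjects with a first abnormality after EOT is not in the documents. As an assumption, take 0 to 3 such subjects in a 12-subject arm with no earlier event, and use the Clopper-Pearson interval of SAP 9.1.1:

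| First seen after EOT | Treatment-period window | EOS window |
|---|---|---|
| 0 | 0% (0 to 26.5) | 0% (0 to 26.5) |
| 1 | 0% (0 to 26.5) | 8.3% (0.2 to 38.5) |
| 2 | 0% (0 to 26.5) | 16.7% (2.1 to 48.4) |
| 3 | 0% (0 to 26.5) | 25.0% (5.5 to 57.2) |

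The denominator in 10.9.4 is subjects with any post-baseline assessment. Under the narrow reading, numerator and denominator can therefore cover different periods.

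**6. Drug remaining at EOS.** Protocol 1.3.2.1 gives a half-life of 12 to 22 days after multiple dosing in healthy subjects. Assuming mono-exponential decline and similar kinetics in SLE, the fraction left after 42 days is 2^(−42/12) = 0.088 to 2^(−42/22) = 0.266, or about 9 to 27%. The follow-up visit is off treatment but not drug-free.

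**The case against.** The best defence is that 10.9.4 sits under 10.9, whose opening rule already takes abnormality summaries to EOS, and that the SAP uses treatment period loosely elsewhere. SAP 10.9.1 and 10.9.2.2 apply the phrase to repeated adverse events, although SAP 5.8.1.1 makes events treatment-emergent up to Visit 7. On that reading nothing is excluded. It is a possible reading, but it does not remove the conflict. Protocol 3.1.1.2 and 3.1.1.3 fix the treatment period at 12 weeks and start follow-up immediately after the last dose. Table 11 also puts EOS in a separate follow-up phase, and the SAP names EOS where it means EOS.

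It is also fair to say that the consequence is limited, and this stands. Values after EOT remain in the by-visit summaries and listings. Clinically relevant abnormalities must be reported as adverse events (Protocol 7.2.1.1) and count as treatment-emergent up to EOS. The safety analysis is mainly descriptive.

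A reader might infer more than the documents support:
- That 5.8.10 runs to EOS throughout. Its low/high sentence names the treatment period.
- That blood-pressure events are lost. The row for any time post-baseline runs to EOS in 5.8.6.1 and 10.9.5, so they are counted there.
- That readings after EOT are drug-free. Step 6 shows otherwise.
- That six of 18 weeks are certainly excluded. That holds only if the treatment period means 12 weeks.

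**Conclusion.** The conflict is in the text and should be resolved before the tables are programmed. It is clearest for liver criteria, where two SAP sections give different windows for one summary. For other marked laboratory abnormalities, the two laboratory sections agree with each other but contradict the SAP's general safety rules and the protocol, without a declared change.

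If 10.9.4 is followed literally, a completer's EOS visit does not contribute to the treatment-emergent laboratory and liver incidence tables. The excluded stretch is 42 days with a 12-week treatment period, or about three weeks with Table 11's treatment phase. In a 12-subject arm, one event first seen at that visit decides between a reported 0% and 8.3%. Whether any such event occurs cannot be known from the documents.

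The blood-pressure point is smaller: one derivation is out of line, and following it would mix off-treatment readings into a single row. The main pharmacodynamic test, its alpha and its power do not depend on any of this.

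**What to change.** Make four short SAP edits:

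1. In 5.8.10, low/high sentence: replace the treatment-period wording with a window from first intake up to EOS (6 weeks after last intake).
2. In 10.9.4, sentence on laboratory abnormalities by severity: the same window.
3. In 10.9.4, sentence on the maximum liver value: the same window, which then matches the liver criteria in 5.8.10.
4. In 11.2.17.1: end the interval after Day 1 at EOT, to match 5.8.6.1, 10.9.5 and 11.1.1. The row for any time post-baseline already covers EOS.

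Changing only 10.9.4 and 11.2.17.1 would not be enough, because the low/high sentence in 5.8.10 would then contradict 10.9.4. The EOS visit has a ±5-day allowance (Protocol 8.3.1), so the new wording should make clear that a visit within that allowance counts. If an on-treatment count is also wanted, add it as a second, labelled column with its end date stated.

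The cost is a few words in the SAP, with no new data and no change to the design.

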#### 10.9.5 Vital signs and body weight

For body weight, a summary table presenting the value at baseline, value at Visit 6 (EOT) and the change from baseline is produced by treatment group.

Standing SBP and DBP (mmHg) are not included in the summary tables but included in the listings.

For supine SBP and DBP (mmHg), the following displays are provided:

- Quantitative descriptive statistics for absolute values by treatment group and analysis visit and time point.
- Quantitative descriptive statistics for the absolute change from baseline to 1h, 2h, 3h, 4h, 5h and 6 h post-dose on Day 1 and each post-baseline analysis visit by treatment group and parameter. This table is repeated for the measurements taken on day of study drug re-initiation, if applicable.
- Boxplots of absolute values at baseline and all post-baseline analysis visits and time points: one figure per parameter and per treatment group. Notable abnormality thresholds are displayed on the plots as an overlay.
- Notable BP abnormalities are summarized by treatment group by presenting the number and percentage of subjects with any abnormality at each post-baseline analysis visit and time point, at any time on Day 1 (from 1 hour post-dose to discharge), at any time after Day 1 (from discharge on Day 1 up to EOT), and at any time post-baseline (from 1 hour post-dose to EOS), 95% Clopper-Pearson confidence intervals are presented for the proportions.

The denominator for percentages is the number of subjects with at least one post-baseline assessment in the considered interval.

All data (values and changes) are listed by treatment group, subject and visit. All marked abnormalities are flagged.

#### 10.9.6 Spirometry

Quantitative descriptive statistics are presented by parameter, by analysis visit and treatment group. In addition, a summary table presenting the absolute change from baseline to each visit up to EOS is produced. Similarly the percent change from baseline to each visit up to EOS are presented by visit and by treatment group.

The number and percentage of subjects with a decrease in FEV1 or FVC of > 15% from baseline value is provided for each visit, by analysis visit and treatment group, each with 95% Clopper-Pearson confidence intervals. In addition, the number and percentage of

subjects with a 15% decrease in FEV1 or FVC at one visit, 2 consecutive visits, 3 consecutive visits, and more than 3 visits during the treatment period is presented.

The evolution of the values over time is provided in graphical format for FEV1 (L), FVC (L) and FEV1/FVC (one figure per parameter: one boxplot per treatment group and analysis visit, from baseline to EOS).

All data (values and changes) are listed by treatment group, subject and visit. All marked abnormalities are flagged.

#### **10.9.7 Physical examination**

A listing presents the findings of physical examination (Clinical significance and details) by treatment group, subject number, body system and visit number.

#### **10.9.8 Ophthalmological examination and OCT**

A listing presents the findings of ophthalmological examination (Clinical significance and details) by treatment group, subject number, visit and by type of examination (optical coherence tomography test, ophthalmological examination).

#### **10.9.9 Echocardiography**

A listing presents the findings of echocardiography (Clinical significance and details) by treatment group, subject number and visit.

### **10.10 Analysis of quality of life variables**

For each score (8 domain scores, 2 component scores), quantitative descriptive statistics are presented for each analysis visit (baseline and EOT) and for the change from baseline to EOT by treatment group for the SAF. Additionally, the mean treatment differences for each ACT-334441 dose compared to placebo and their corresponding 95% CIs are provided using an ANOVA with treatment group as a factor in the model.

If the data are non-normally distributed or should the assumptions underlying the ANOVA model (normality of the residuals, homogeneity of the variance) not be fulfilled, the same comparisons between treatment groups will also be performed using a non-parametric one-way ANOVA.

For the reported health transition item, qualitative descriptive statistics are presented for each visit by treatment group.

### **10.11 Analysis of pharmacokinetic variables**

For PK variables [defined in Section 5.6], quantitative descriptive statistics (including geometric mean and 95% CI) for ACT-334441 plasma concentrations are presented by visit and treatment group for the PKS. It includes only data from samples that are taken according to the protocol i.e.,

- For Week 2, 4 and 8: trough samples, i.e., samples taken before dosing and one day after the previous dose
- For Week 12: samples taken within 1 to 7 days following the last dose.

The evolution of the values over time is provided in graphical format (one figure: one boxplot per treatment group and analysis visit, from baseline to EOS).

A listing of individual data is produced on the SCR.

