## **LIST OF ABBREVIATIONS AND ACRONYMS**

|              |   |
|--------------|---|
| ACR          | American College of Rheumatology                                |
| AE           | Adverse event   |
| AESI         | Adverse event of special interest                               |
| ALT          | Alanine aminotransferase  |
| ALP          | Alkaline Phosphatase  |
| ANA          | Anti-nuclear antibodies   |
| ANCOVA       | Analysis of covariance  |
| anti-dsDNA   | Anti-double-stranded deoxyribonucleic acid                      |
| APL          | Immunoglobulin A Phospholipid                                   |
| AST          | Aspartate aminotransferase                                      |
| ATC          | Anatomic therapeutic chemical                                   |
| BLyS         | B-lymphocyte stimulator   |
| BP           | Blood pressure  |
| bpm          | Beats Per Minute  |
| CCM          | Central Clinical Monitoring                                     |
| CI           | Confidence interval   |
| CRP          | C-reactive protein  |
| CL           | Confidence limit(s)   |
| CSR          | Clinical study report   |
| CTCAE        | Common Terminology Criteria for Adverse Events                  |
| $C_{trough}$ | Measured plasma concentration at the end of one dosing interval |
| CXCL10       | C-X-C motif chemokine 10  |
| DBP          | Diastolic blood pressure  |
| ECG          | Electrocardiogram   |
| eCRF         | Electronic case report form                                     |
| EDTA         | Ethylenediaminetetraacetic acid                                 |
| $E_{max}$    | Maximum effect  |

|                  |  |
|------------------|--|
| EOS              | End-of-study                                 |
| EOT              | End-of-treatment                             |
| FAS              | Full analysis set                            |
| FDA              | (US) Food and Drug Administration            |
| FEV 1 | Forced expiratory volume in 1 second         |
| FSFV             | First subject first visit                    |
| FU               | Follow-up                                    |
| FVC              | Forced vital capacity                        |
| GPL              | Immunoglobulin G Phospholipid                |
| HIV              | Human immunodeficiency virus                 |
| HR               | Heart rate                                   |

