### 5.6 Pharmacokinetic variables

PK samples are collected at Visit 3 (Week 2), Visit 4 (Week 4), Visit 5 (Week 8), Visit 6 (Week 12/ EOT), and Visit 7 (EOS).

PK variables comprise

- $C_{trough}$  ACT-334441 plasma concentrations prior to dosing at Weeks 2, 4, 8, and 12 (EOT);
- ACT-334441 plasma concentration at EOS (i.e., 6 weeks after study treatment discontinuation).

The following PK endpoint is defined:

- Cenerimod (ACT-334441) plasma concentrations at each analysis visit.

For analysis visits Weeks 2, 4, 8, samples must be taken 1 calendar day after the previous dose and before the next dose (see Section 11 for details of how this is handled).

For analysis visit Week 12, samples must be taken within 1 to 7 calendar days after the last dose (see Section 11 for details of how this is handled).

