### 11.2.20 Pharmacokinetics Concentrations Data

The dataset contains the information from the Pharmacokinetics Concentration (PC) and its supplemental domain, in a basic data structure.

**Analysis value** is defined as the value at the visit (numeric result in standard units). Original results recorded as below the lower limit of quantification (LLOQ) are set to zero.

**Analysis Relative Time** is defined, for Visits 3 to 5, as the amount of time between the PK sample and the next study drug intake, expressed in minutes (**Analysis Relative Time Unit** is defined as 'MINUTES').

**Analysis Relative Day** is defined, for Visits 3 to 7, as the number of days elapsed between the last dose and the PK sampling.

In addition to the **Analysis Record Flag** populated as described in the general section, a second **Analysis Record Flag** is created to identify samples taken under the expected conditions i.e.,

- For analysis of Visits 3 to 5: samples taken before the morning dose and one day after the last dose
- For analysis visits Week 12 and EOT: samples taken within 1 to 7 days following the last dose.

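### Week 12 is listed as a trough concentration but admits samples up to 7 days after the last dose, so it is not like-for-like with Week 8 if any sample is late

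*SAP*

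**What the plan says.** The first pharmacokinetic variable in SAP 5.6 is C_trough at Weeks 2, 4, 8 and 12 (EOT), all described as taken before dosing. Protocol 6.3 and 11.3.4 list the same time points. The SAP's list of abbreviations defines C_trough as "Measured plasma concentration at the end of one dosing interval".

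The sampling rules then differ by visit:

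- **Weeks 2, 4 and 8.** SAP 5.6: "For analysis visits Weeks 2, 4, 8, samples must be taken 1 calendar day after the previous dose and before the next dose". SAP 10.11 repeats this: "For Week 2, 4 and 8: trough samples, i.e., samples taken before dosing and one day after the previous dose".
- **Week 12.** SAP 5.6: "For analysis visit Week 12, samples must be taken within 1 to 7 calendar days after the last dose". SAP 10.11: "For Week 12: samples taken within 1 to 7 days following the last dose". SAP 11.2.20, which defines the analysis flag: "For analysis visits Week 12 and EOT: samples taken within 1 to 7 days following the last dose".

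The 7-day limit is the protocol's window for the EOT visit. Protocol 3.1.1.2 and 8.2.4 aim for one day after the last dose and allow at most 7. Protocol 7.3.2 exempts EOT from pre-dose sampling.

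SAP 10.11 summarises concentrations by visit and treatment group, with geometric mean and 95% CI, and plots all visits in one boxplot figure. No Week 12 summary limited to one-day samples is planned.

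**The concern.** Dosing is once daily, so a trough is a sample about one day after the previous dose. Once dosing stops, concentration only declines. A Week 12 sample on days 2 to 7 is therefore an elimination-phase value, and pooling it with one-day samples pulls the Week 12 summary below the true trough.

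The by-visit table and figure are the planned description of exposure in SLE, which is a stated exploratory objective. In both, Week 12 stands beside Week 8 under a different timing rule. If some Week 12 samples are late, an apparent fall from Week 8 to Week 12 could be a timing artefact, and nothing in the planned summaries would separate it from a real change.

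**Working it through.** The plan states no figure for this point, so there is none to reproduce. The check sizes the effect of a late sample.

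**Inputs**

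- Week 12 window: 1 to 7 days after the last dose (SAP 5.6, 10.11, 11.2.20).
- Half-life after the last of multiple doses: 12 to 22 days (Protocol 1.3.2.1, healthy subjects).
- Time to steady state: 20 to 32 days (same section).
- Planned group size: 12 per active dose (Protocol 3.1).
- Share of late samples: not in the documents, so shown as a range.

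**One late sample.** Assume mono-exponential decline at the stated half-life. The ratio of a day-d sample to a day-1 sample is 2^(−(d−1)/t½).

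| Sample day | t½ = 12 days | t½ = 22 days | Lower by |
|---|---|---|---|
| 2 | 2^(−1/12) = 0.944 | 2^(−1/22) = 0.969 | 3–6% |
| 4 | 2^(−3/12) = 0.841 | 2^(−3/22) = 0.910 | 9–16% |
| 7 | 2^(−6/12) = 0.707 | 2^(−6/22) = 0.828 | 17–29% |

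**Group geometric mean.** If a fraction f is sampled at day 7 and the rest at day 1, the geometric mean is multiplied by (day-7 ratio)^f.

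- f = 10%: 0.707^0.10 = 0.966 and 0.828^0.10 = 0.981, so 2–3% lower.
- f = 25%: 0.707^0.25 = 0.917 and 0.828^0.25 = 0.954, so 5–8% lower. In a group of 12 this is three subjects.
- f = 50%: 0.841 and 0.910, so 9–16% lower. Timing spread evenly over days 1 to 7 gives the same result, because the mean delay is 3 days.
- f = 0: no effect.

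**Which comparison is affected.** The Week 2 target is day 15 (SAP Table 11), before the stated 20–32 days to steady state, and the Week 4 target, day 29, falls inside that range. Those visits may differ from Week 12 because of accumulation, in the opposite direction. Weeks 8 and 12 both lie beyond the range, so little true change is expected between them, and a timing effect would show there most clearly.

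**Pairing with the lymphocyte count.** SAP 5.5.1 accepts an EOT count in the pharmacodynamic and per-protocol sets up to 7 days after the last intake. That is the same upper limit, and Protocol 8.2.4 has both samples drawn at the EOT visit, so a late concentration is matched by an equally late count.

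**The case against.** The strongest reply is that the SAP is open about the difference. SAP 10.11 uses the word trough only for Weeks 2, 4 and 8 and describes Week 12 by its window. SAP 5.6 also defines the analysed endpoint simply as the plasma concentration at each analysis visit. The window is the protocol's own, and one day after the last dose is the intended timing, which carries no bias. SAP 11.2.20 derives days since last dose, and individual values are listed. Pharmacokinetics is exploratory and descriptive, and no test compares visits.

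Most of this stands, and it limits the point. It does not remove the mismatch: SAP 5.6 still names Week 12 as a pre-dose C_trough, and following the protocol's visit window makes a sample admissible without making it a trough. Late samples are also foreseeable. Protocol 5.1.9 asks subjects who stop early to return within 7 days, and those who stop late enough fall in the Week 12 analysis window of days 71–105.

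Several stronger readings are tempting, but the documents do not support them:

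- *Week 12 is biased low and cannot be compared with earlier visits.* The rule permits late samples; nothing shows that they are common.
- *The loss at day 7 is far larger.* The single-dose half-life (170–199 h, or 7.1–8.3 days) gives 39–44%, but it is not the half-life stated for decline after repeated dosing. Back-calculating a half-life of 3.1–5.9 days from the 5- to 9-fold accumulation gives 51–74%. That needs a one-compartment model which the documents do not state, and it conflicts with their 12–22 days.
- *Steady-state and dose-proportionality checks are distorted.* No such analysis is planned. Dose groups share the same Week 12 window, so a between-dose distortion would need lateness to differ by dose.
- *The concentration no longer matches the EOT lymphocyte count.* The shared 7-day limit keeps them matched.

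**Conclusion.** The concern holds as a mismatch between label and rule with a one-directional effect. The Week 12 row is called C_trough, but its inclusion rule admits values that are not troughs, and any such value lowers the row relative to a true trough. At the stated multiple-dose half-life the shift is 17–29% for a day-7 sample and 3–6% for a day-2 sample. It is about 5–8% on a group geometric mean if 25% are sampled at day 7.

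These figures assume mono-exponential decline at 12–22 days from the first day after the last dose, and that the healthy-subject half-life carries over to SLE. If the early decline is steeper, they understate the effect. The share of late samples is unknown; if every subject attends one day after the last dose, the effect is nil.

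What is affected is the descriptive Week 8 versus Week 12 comparison. The main pharmacodynamic endpoint, its test and the sample size do not depend on it.

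**What to change.** In SAP 5.6, 10.11 and 11.2.20:

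- Restrict the Week 12 C_trough summary and its box in the figure to samples taken one calendar day after the last dose, using the days-since-last-dose variable that 11.2.20 already derives for Visits 3 to 7.
- Report the full 1–7 day set separately, labelled EOT concentration, with days since last dose. This keeps every sample and preserves the pairing with the EOT lymphocyte count.
- At minimum, relabel the present Week 12 row and add the restricted summary beside it.

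The cost is SAP wording, one changed condition on the second analysis record flag in 11.2.20, and one extra summary row. Dosing and sampling times are already collected under Protocol 7.3.2. The downside is somewhat fewer samples in the Week 12 trough row, by however many were late.
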